## 3 EXPERIMENTAL PLAN

### 3.1 STUDY DESIGN

This is a multicenter, placebo-controlled, randomized, dose escalation, safety, and tolerability study of UNEX-42 in infants born at <27 weeks of GA at high risk for BPD. UNEX-42 will be administered via IV infusion to 3 cohorts at 20, 60, and 200 pmol phospholipid/kg body weight. Within each cohort, eligible subjects will be randomly assigned to receive either UNEX-42 or placebo treatment (2:1 allocation ratio). A schematic presentation of the study design is presented in [Figure 3-1](#).

**Figure 3-1 Schematic of Study Design for an Individual Subject**

\*Subjects that discontinue the study prematurely should have the 40 Weeks Postmenstrual Age/Hospital Discharge assessments performed if possible. Subjects that complete the 40 Weeks PMA Assessment or are discharged from hospital will continue into the Long-term Outcome Phase.

Study assessments will occur during the study at the following time points: Screening, Baseline, 24 and 72 hours postdose, 7 days postdose, weekly until 35 weeks PMA, 36 weeks PMA, and 40 weeks PMA/hospital discharge during the Post-treatment Phase. For subjects that complete the Post-treatment Phase, the Long-term Outcome Phase will occur at 6 months (phone contact) and 1 year of corrected age (site visit).

### 3.2 OVERALL SCHEDULE OF TIMES AND EVENTS

**Table 3-1 Schedule of Times and Events – Post-treatment Phase**

Study Procedures	Screening a	Baseline a	Post-treatment Phase					
			24 Hours Postdose	72 Hours Postdose	7 Days Postdose	Weekly Until 35 Weeks PMA	36 Weeks PMA b	40 Weeks PMA/ Hospital Discharge b,c
Study Day	-48 Hours to Baseline	1	2	4	8	15, 22, 29, 36, 43, 50, 57, 64, 71, 78, and 85	50 up to 88	78 up to 116
Visit Window			±4 hours	±4 hours	±1 day	±2 days	±2 days	±2 days
Parental Informed Consent	X							
Subject Eligibility	X	X						
Medical History	X							
Demographics	X							
Maternal History	X							
Weight	X	X				X	X	X
Length and Head Circumference		X					X	X
CXR d		X					X	
Clinical Laboratory Assessments e		X		X			X	
Predefined Complications of Prematurity		X	X	X	X	X	X	X
Vital Signs f		X	X	X	X	X	X	X
Physical Examination		X					X	
Mean Airway Pressure g		X	X	X	X	X	X	X
Oxygen Saturation h		X	X	X	X	X	X	X
Respiratory Severity Score i		X	X	X	X	X	X	X
Tracheal Aspirate j		X		X	X			
Concomitant Medications		X	X	X	X	X	X	X
Adverse Events k	X	X	X	X	X	X	X	X
Randomization		X l						
UNEX-42/Placebo Administration		X l						
Incidence and Severity of BPD m							X	

Study Procedures		Screening a	Baseline a	Post-treatment Phase					
Assessment Period	Study Day			24 Hours Postdose	72 Hours Postdose	7 Days Postdose	Weekly Until 35 Weeks PMA	36 Weeks PMA b	40 Weeks PMA/ Hospital Discharge b,c
Study Day		-48 Hours to Baseline	1	2	4	8	15, 22, 29, 36, 43, 50, 57, 64, 71, 78, and 85	50 up to 88	78 up to 116
Visit Window				±4 hours	±4 hours	±1 day	±2 days	±2 days	±2 days
Duration of Mechanical Ventilation, Supplemental Oxygen Therapy, and Hospitalization									X n

Abbreviations: AE, adverse event; CXR, chest x-ray; FiO2, fraction of inspired oxygen; GA, gestational age; PMA, postmenstrual age; RSS, Respiratory Severity Score

a The Screening and Baseline assessments may be combined; however, all entry criteria must be confirmed prior to randomization.

b The days of the 36 and 40 Weeks PMA assessments are based on each subject's GA determined during Screening based on local standard practice.

c Subjects that discontinue the study prematurely should have the 40 Weeks PMA/Hospital Discharge assessments performed if possible. Subjects that complete the 40 Weeks PMA assessment or are discharged from hospital will continue into the Long-term Outcome Phase shown in [Table 3-2](#).

d The most recent CXRs prior to randomization and 36 Weeks PMA can be used.

e Clinical laboratory assessments will consist of a complete blood count, differential count, sodium, potassium, chloride, bicarbonate, blood urea nitrogen, creatinine, aspartate aminotransferase, alanine aminotransferase, and total and indirect bilirubin. For Baseline, the clinical laboratory assessments may utilize the laboratory assessments obtained as standard of care treatment within the last 24 hours in lieu of drawing blood for the sole purpose of the study. Any study-required blood tests should be obtained at the same time a blood sample is being collected for clinical purposes, if possible.

f On Day 1, vital signs are to be collected just prior to dosing, at the midpoint of dosing, just after the end of dosing, and at least once every hour for the first 4 hours after dosing is completed. Vital signs are to include heart rate, respiratory rate (either spontaneous rate or the sum of spontaneous rate and mechanically delivered rate), and systemic blood pressure (systolic and diastolic).

g Mean airway pressure is only to be collected from subjects undergoing mechanical ventilation.

h Oxygen saturation should be measured from a post-ductal location and should be consistently obtained post-ductally throughout the study period.

i The RSS should be calculated as the mean airway pressure multiplied by FiO2. Mean airway pressure and FiO2 will be collected at the same time, and the RSS will only be calculated when the subject has an obtainable mean airway pressure.

j A tracheal aspirate will be collected as possible at Baseline (prior to dosing), 72 hours postdose (if still intubated), and 7 days postdose (if still intubated).

k All AEs will be documented from the time of informed consent until the time screen failure is documented, or until the subject is either discontinued from the study or all 40 Weeks PMA/Hospital Discharge assessments have been completed and should be followed until either resolution (or return to normal or baseline values), until they are judged by the Investigator to no longer be clinically significant, or for at least 30 days if the AE extends beyond the Post-treatment Phase.

l UNEX-42 or placebo will be administered after all other Day 1 assessments are completed, with the exception of vital signs (see footnote f).

m This assessment to be performed at 36 Weeks PMA or at Hospital Discharge, whichever comes first (see Section [3.3.1](#)).

n For each parameter, the total number of days from Baseline to the 40 Weeks PMA/Hospital Discharge will be calculated.

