**3.3.2.3 Vital Signs**

Vital signs will be collected during all study assessment timepoints from Baseline to 40 Weeks PMA/Hospital Discharge. On Day 1, vital signs are to be collected 7 times: just prior to dosing, at the midpoint of dosing, just after the end of dosing, and at least once every hour for the first 4 hours after the completion of dosing.

Vital signs measured will include systemic blood pressure (systolic and diastolic), heart rate, and respiratory rate (either spontaneous rate or the sum of spontaneous rate and mechanically delivered rate). Except for dose administration, no other measurements or procedures should be performed during measurement of vital signs. Vital signs should also be assessed in the case of abnormal clinical signs and symptoms.

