#### 4.1 INCLUSION CRITERIA

A subject must meet the following criteria to be eligible for the study:

1. Infant whose postnatal age is 3 to 14 days at randomization.
2. Subject meets the following oxygen and birth weight criteria based on GA:

Gestational Age at Birth	Criteria
23 weeks to 24 weeks 6 days	Any birth weight, any oxygen requirement
25 weeks to 26 weeks 6 days	$\text{FiO}_2 \geq 35\%$ (sustained >2 hours) at any point during postnatal Days 1 to 14 AND birth weight $\leq 750$ g

3. Endotracheally intubated and receiving mechanical ventilation at the time of Screening and randomization.
4. Not expected to be extubated within the next 24 hours after randomization.
5. The subject has a parent/guardian who gives written informed consent.

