## 6.2 SELECTION OF DOSES FOR SUBJECT COHORTS

The starting dose for Cohort 1 of 20 pmol phospholipid/kg body weight was selected as described in Section 1.3. Dose administration for each cohort will occur such that there is an observational period of 3 days between dosing the first, second, and third subject. This observational period will allow for the monitoring of any dose-limiting toxicities (DLTs) (see Section 6.3) in at least 1 subject treated with UNEX-42. The Data Monitoring Committee

(DMC) will make dose escalation recommendations based on review of safety data between cohorts (see Section 10.7).

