### **6.3 DOSE-LIMITING TOXICITY**

DLTs will be used to inform dosing decisions; however, no DLTs have been observed during nonclinical development of UNEX-42. Therefore, for the purposes of this study, only an estimate of possible dose-limiting events can be made. As a result, DLTs will be defined as any of the following toxicities assessed by the Investigator and/or Sponsor as at least possibly related to UNEX-42 based on the time to onset following UNEX-42 administration and judged not to be related to the underlying condition or any concomitant medications by the Investigator and/or Sponsor:

- A treatment-emergent adverse event (TEAE) that is of potential clinical significance such that further dose escalation would expose subjects to unacceptable risk.
- Increased liver enzymes (Grade 2 or higher, using the National Cancer Institute (NCI) Common Terminology Criteria for Adverse Events (CTCAE) Version 5.0 as guidance) or any evidence of hepatic failure.
- Pulmonary toxicity, worsening respiratory distress, or other acute exacerbation of pulmonary function requiring ventilatory support or escalation of care.

In addition, the DMC may identify as a DLT, any TEAE occurring in subjects treated with UNEX-42 at any time during the study. Each DLT must be recorded in the eCRF as an AE. In addition, any DLT that meets criteria for a SAE must be reported to the Sponsor in an expedited manner as described in Section 9.4.

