### 10.3.1 Primary Endpoints

The primary endpoints are the following safety assessments during the Post-treatment Phase:

- Incidence of TEAEs
- Incidence of all-cause mortality through Week 36 PMA
- Incidence of treatment-related AEs
- Absolute and changes from Baseline in laboratory parameters
- Absolute and changes from Baseline in vital signs

All AEs as recorded by the Investigator will be assigned a Medical Dictionary for Regulatory Activities (MedDRA) preferred term and system organ class by the Sponsor for reporting purposes. Summaries of AEs and deaths will include the number and percentage of subjects who experienced these events for each dose cohort and placebo. AEs will be further summarized by preferred term and system organ class for each dose cohort and placebo.

Descriptive statistics (mean, standard deviation, median, interquartile range, minimum, and maximum) will be computed by treatment group and overall for measured values and change from Baseline of clinical laboratory parameters and vital signs.

Summaries of safety data will be descriptive with no inferential analyses planned.

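### Every infant is ventilated at randomization, yet no FiO2, mean airway pressure, oxygen saturation or RSS reading is scheduled from the start of dosing until the 24-hour visit

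*Protocol*

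**What the plan says.** Inclusion criterion 3 (Protocol 4.1) requires intubation and mechanical ventilation at Screening and at randomization. Criterion 4 adds: "Not expected to be extubated within the next 24 hours after randomization".

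Table 3-1 schedules mean airway pressure, oxygen saturation and RSS at Baseline, at 24 hours ±4 hours, at 72 hours ±4 hours, and later. RSS is mean airway pressure times FiO2. FiO2 has no row of its own and is taken together with mean airway pressure (footnote i). Footnote l fixes the order on Day 1: "UNEX-42 or placebo will be administered after all other Day 1 assessments are completed, with the exception of vital signs".

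Vital signs are the one assessment repeated around dosing, seven times on Day 1. Section 3.3.2.3 gives their content: "Vital signs measured will include systemic blood pressure (systolic and diastolic), heart rate, and respiratory rate". Footnote f specifies "respiratory rate (either spontaneous rate or the sum of spontaneous rate and mechanically delivered rate", so a recorded rate may include ventilator breaths. Section 3.3.2.3 also bars other measurements, dosing apart, while vital signs are being taken.

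The protocol does treat acute respiratory harm as a risk. Section 6.1 lists acute respiratory deterioration among the reasons to stop an infusion. Section 6.3 counts the following as a dose-limiting toxicity (DLT), if judged possibly due to the product and not otherwise explained: "Pulmonary toxicity, worsening respiratory distress, or other acute exacerbation of pulmonary function requiring ventilatory support or escalation of care".

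For the review between cohorts, Section 10.4 points the DMC to the endpoints in Section 10.3.1. RSS is in Section 10.3.2, with the secondary endpoints.

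**The concern.** This is the first clinical use of UNEX-42, given intravenously to infants who already depend on a ventilator. In such an infant, an acute lung reaction would be expected to show in the oxygen and airway pressure needed and in the saturation achieved. The Day 1 schedule follows the circulation closely and leaves those three unmeasured after dosing.

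A worsening that starts and settles before the 24-hour visit would leave no scheduled reading. Whether it is recorded then depends on someone judging it to be an adverse event, and whether it counts as a DLT depends on a further judgement that the underlying lung disease did not cause it. Both judgements are hard in this population. Measured values in active and placebo infants would let the DMC set those judgements against data before the dose rises to 60 and then 200 pmol/kg.

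**Working it through.** **Inputs.** Seven Day 1 vital-sign sets: before dosing, midpoint, end, and hourly to 4 hours (Protocol 3.3.2.3). Dose volume 1 mL at 10 mL/hour (6.1). First post-dose visit at 24 hours ±4 hours and second at 72 hours ±4 hours (Table 3-1). Cohorts of 6, with 4 active and 2 placebo (3.5).

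**The plan's own count.** 1 before + 1 midpoint + 1 end + 4 hourly = 7, which agrees with Section 3.3.2.3. After dosing starts: 7 − 1 = 6.

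**Timing.** Infusion: 1 mL ÷ 10 mL/hour = 0.1 hour = 6 minutes, with the midpoint at 3 minutes. The line flush is extra, and its volume is not stated. First post-dose support reading: 24 − 4 = 20 hours to 24 + 4 = 28 hours. If postdose time runs from the end of infusion, that is 20.1 to 28.1 hours from its start.

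| Time | Blood pressure, heart rate, respiratory rate | FiO2, mean airway pressure, saturation, RSS |
|---|---|---|
| Before dosing | yes | yes (Baseline) |
| Midpoint, end, 1, 2, 3 and 4 hours | yes (6 sets) | none |
| 24-hour visit (20 to 28 hours) | yes | yes |

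Scheduled support readings from the start of dosing to 20 hours: 0. With readings beside the six existing sets: 6. The longest stretch without one falls from 20–28 hours to 16–24 hours (20 − 4 and 28 − 4).

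**Before the next infant is dosed.** Section 6.2 says "there is an observational period of 3 days between dosing the first, second, and third subject". Assume this means exactly 72 hours. The 72-hour visit runs from 68 to 76 hours, so it may fall after the next dose. Only the 24-hour reading is then sure to come first: 1 now, and 1 + 6 = 7 with the change. This is a worst case for the present schedule, and all six added readings lie within about 4 hours of the infusion.

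**DMC items.** Section 10.3.1 lists five: treatment-emergent events, mortality, treatment-related events, laboratory values and vital signs. None names FiO2, mean airway pressure or RSS. The protocol's description of vital signs does not name saturation. SAP 11.5 lists saturation alongside vital signs, but only at the times it was collected, so it adds no Day 1 time point.

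**The case against.** The strongest reply is that the infants are closely watched and that harm has several routes into the record. Adverse events are documented continuously from consent. Worsening of an existing condition can be an adverse event, and events of any cause are compared by group: "AEs will be further summarized by preferred term and system organ class for each dose cohort and placebo". The DMC is not bound by the investigator's attribution: "the DMC may identify as a DLT, any TEAE occurring in subjects treated with UNEX-42 at any time during the study". Vital signs are also taken when clinical signs are abnormal. SAP 11.6 lists respiratory support by type, with oxygen percentage at start and stop, and SAP 8 adds assessment times where available. All of this stands. It means that respiratory harm can be recorded and acted on. These routes depend on an event occurring and being reported, though, so they do not give values at common times in both arms.

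Second, the Section 10.4 list is of endpoints of interest and is not exclusive. The DMC reviews the data available, and its charter and separate analysis plan are not in the documents. A reader might infer that the DMC would be refused respiratory support data. The documents do not support that. They show only that the protocol does not name such data.

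Third, each cohort has 4 active and 2 placebo infants, and no threshold is proposed, so a by-arm table would be descriptive only. That is true, and it holds for every safety summary in this study.

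Fourth, added readings would on their face breach the rule in Section 3.3.2.3 against other measurements during vital signs. This also stands, and any change has to deal with it.

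**Conclusion.** The schedule gap is real and follows directly from Table 3-1 and its footnotes. There are 0 scheduled readings of FiO2, mean airway pressure, saturation or RSS from the start of dosing to 20 hours, against six sets of circulatory signs and respiratory rate in the first 4 hours. What is missing is an early, objective respiratory measure, taken at fixed times in both arms and free of attribution. The DMC part is weaker: RSS is not among the protocol's named review items, but the charter may include it.

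A reader might infer that the plan is blind to respiratory harm, or that infants go unobserved from 4 to 20 hours. Neither follows, because event recording is continuous and routine care goes on throughout.

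The conclusion assumes that Table 3-1 is the complete schedule and that the case report form, which is not in the documents, adds no Day 1 readings. SAP 1.1 records that the study ended with 3 subjects randomized in a partly filled first cohort and that only listings will be produced. No planned group comparison is affected. This is an inexpensive improvement for the protocol design or a successor study.

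**What to change.** 1. Amend footnotes f and l of Table 3-1 and Section 3.3.2.3 so that FiO2, mean airway pressure and post-ductal saturation are read from the ventilator and monitor just before or just after each of the six vital-sign sets from mid-infusion to 4 hours. Alternatively, exempt these passive readings from the rule against other measurements. The exemption may suit the midpoint and end sets better, since they are about 3 minutes apart. Calculate RSS from the readings. Criterion 4 makes it likely that infants are still intubated, so mean airway pressure should be obtainable.
2. In Section 10.4, name these values and their change from Baseline, by arm and whatever the attribution, among the DMC review items, unless the charter already does so.

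Cost: 6 sets × 3 values = 18 more recorded values per infant, 18 × 6 = 108 per cohort and 18 × 18 = 324 at full enrolment. Add one changed sentence in Section 3.3.2.3, two footnote edits and one DMC table, which the independent consultant who already prepares the DMC analyses (Section 10.7) could produce. No blood draw or extra visit is needed. The change does not cover 4 to 20 hours, or 16 of the first 20 hours, which would still rely on routine care and adverse event reporting.

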**Table 3-2 Schedule of Times and Events – Long-term Outcome Phase**

Study Procedures	Long-term Outcome Phase	
Assessment Period	6 Months (Corrected Age) Phone Contact a	1 Year (Corrected Age) Visit b
Study Day	Calculated	Calculated
Visit Window	±2 weeks	±4 weeks
Weight, Length, and Head Circumference		X
Serious Adverse Reactions c	X	X
Assessment of General Health	X	X

Abbreviations: PMA, postmenstrual age

a To be performed at 6 months corrected age for all subjects, as possible, including those discharged from the hospital prior to 40 Weeks PMA. See Section [7.5](#).

b To be performed at 1 year corrected age for all subjects, as possible, including those discharged from the hospital prior to 40 Weeks PMA. See Section 7.5.

c Refer to Section [9.1.3](#) for the definition of serious adverse reactions.

### 3.3 CLINICAL ASSESSMENTS

#### 3.3.1 Efficacy

##### 3.3.1.1 Incidence and Severity of Bronchopulmonary Dysplasia

A clinical diagnosis of BPD for infants born <32 weeks of GA is defined by the requirement for supplemental oxygen (>21%) for at least 28 days. Furthermore, the severity of BPD is classified as mild, moderate, or severe based on the level of supplemental oxygen needed at 36 weeks PMA as shown in Table 3-3. This assessment is performed at the 36 Weeks PMA or Hospital Discharge assessment, whichever comes first (Jobe 2001). Supplemental oxygen percentage will be adjusted for altitude when recorded, as necessary.

**Table 3-3 Definition of Bronchopulmonary Dysplasia: Diagnostic Criteria for Gestational Age at Birth <32 Weeks**

BPD Severity	Criteria (Treatment with oxygen >21% for at least 28 days plus)
Mild BPD	Breathing room air at 36 weeks PMA or hospital discharge, whichever comes first
Moderate BPD	Need for <30% oxygen at 36 weeks PMA or hospital discharge, whichever comes first
Severe BPD	Need for ≥30% oxygen and/or positive pressure (positive-pressure ventilation or nasal continuous positive airway pressure) at 36 weeks PMA or hospital discharge, whichever comes first

Abbreviations: BPD, bronchopulmonary dysplasia; PMA, postmenstrual age

##### 3.3.1.2 Duration of Hospitalization

The total number of days between Baseline and the 40 Weeks PMA/Hospital Discharge assessment will determine the duration of hospitalization.

##### 3.3.1.3 Duration of Mechanical Ventilation

Duration of mechanical ventilation (invasive or noninvasive) will be determined by the total number of days (consecutive or nonconsecutive) that an infant receives ventilatory support between Baseline and the 40 Weeks PMA/Hospital Discharge assessment.

##### 3.3.1.4 Duration of Supplemental Oxygen Therapy

The number of days of supplemental oxygen therapy use (consecutive or nonconsecutive) will be determined between Baseline and the 40 Weeks PMA/Hospital Discharge assessment.

### **3.3.1.5    Respiratory Severity Score**

The Respiratory Severity Score (RSS) will be calculated as the mean airway pressure multiplied by fraction of inspired oxygen (FiO2). Mean airway pressure and FiO2 will be collected at the same time, and the RSS will only be calculated when the subject has a mean airway pressure that can be obtained. The RSS will be monitored throughout the Post-treatment Phase.

### **3.3.1.6    Duration of Postnatal Steroids**

Duration of postnatal steroids for purposes of preventing and/or treating BPD (eg, hydrocortisone, dexamethasone, methylprednisolone) will be monitored through 40 Weeks PMA/Hospital Discharge. Postnatal steroid use will be collected as part of the concomitant medication evaluation (see Section 4.3.1).

### **3.3.1.7    Tracheal Aspirate Inflammatory Biomarkers**

A tracheal aspirate will be collected, as possible, at Baseline (prior to dosing), 72 hours postdose (if still intubated), and 7 days postdose (if still intubated). Tracheal aspirates will be evaluated at the local laboratory, as possible, for cell count and differential.

